## 12.10.6. Efficacy Figures

Efficacy: Figures					
No.	Population	IDSL / Example Shell	Title	Programming Notes	Deliverable [Priority]
Primary Endpoint: Loss of Asthma Control					
2.1.	mITT_LoC		Plot of Loss of Asthma Control Over Weeks 0-16 (Primary Estimand)	Include overall and components of loss on control	ETP, SAC
2.2.	mITT_LoC		Plot of Loss of Asthma Control Over Weeks 0-16 (Secondary Estimand)	Include overall and components of loss on control	ETP, SAC
2.3.	mITT_LoC		Cumulative Density Plot of the Posterior Distribution for Loss of Asthma Control Over Weeks 0-16 (Primary Estimand)		ETP, SAC
2.4.	mITT_LoC		Cumulative Density Plot of the Posterior Distribution for Loss of Asthma Control Over Weeks 0-16 (Secondary Estimand)		ETP, SAC
2.5.	mITT_LoC		Plot of Loss of Asthma Control Over Weeks 0-6 (Primary Estimand)	Include overall and components of loss on control	ETP, SAC
2.6.	mITT_LoC		Plot of Loss of Asthma Control Over Weeks 0-6 (Secondary Estimand)	Include overall and components of loss on control	ETP, SAC
2.7.	mITT_LoC		Cumulative Density Plot of the Posterior Distribution for Loss of Asthma Control Over Weeks 0-6 (Primary Estimand)		ETP, SAC
2.8.	mITT_LoC		Cumulative Density Plot of the Posterior Distribution for Loss of Asthma Control Over Weeks 0-6 (Secondary Estimand)		ETP, SAC
Secondary Endpoint: Time to Loss of Control					
2.9.	mITT_LoC		Kaplan-Meier Plot of Time to Loss of Asthma Control (Primary Estimand)		ETP, SAC
2.10.	mITT_LoC		Kaplan-Meier Plot of Time to Loss of Asthma Control (Secondary Estimand)		ETP, SAC

Efficacy: Figures					
No.	Population	IDSL / Example Shell	Title	Programming Notes	Deliverable [Priority]
Secondary Endpoint: Secondary Analysis of Loss of Asthma Control					
2.11.	mITT_LoC		Cumulative Density Plot of Eosinophils		ETP, SAC
2.12.	mITT_LoC		Loss of Control Over Weeks 0-16 vs Eosinophils by Treatment – Fractional Polynomial Model (Primary Estimand)		ETP, SAC
2.13.	mITT_LoC		Loss of Control Over Weeks 0-16 vs Eosinophils – Fractional Polynomial Treatment Difference (Primary Estimand)		ETP, SAC
2.14.	mITT_LoC		Loss of Control Over Weeks 0-16 vs Eosinophils by Treatment – Fractional Polynomial Model (Secondary Estimand)		ETP, SAC
2.15.	mITT_LoC		Loss of Control Over Weeks 0-16 vs Eosinophils – Fractional Polynomial Treatment Difference (Secondary Estimand)		ETP, SAC
2.16.	mITT_LoC		Loss of Control Over Weeks 0-6 vs Eosinophils by Treatment – Fractional Polynomial Model (Primary Estimand)		ETP, SAC
2.17.	mITT_LoC		Loss of Control Over Weeks 0-6 vs Eosinophils – Fractional Polynomial Treatment Difference (Primary Estimand)		ETP, SAC
2.18.	mITT_LoC		Loss of Control Over Weeks 0-6 vs Eosinophils by Treatment – Fractional Polynomial Model (Secondary Estimand)		ETP, SAC
2.19.	mITT_LoC		Loss of Control Over Weeks 0-6 vs Eosinophils – Fractional Polynomial Treatment Difference (Secondary Estimand)		ETP, SAC
2.20.	mITT_LoC		Loss of Control Over Weeks 0-16 vs IgE by Treatment - Fractional Polynomial Model (Primary Estimand)		ETP, SAC
2.21.	mITT_LoC		Loss of Control Over Weeks 0-16 vs IgE – Fractional Polynomial Treatment Difference (Primary Estimand)		ETP, SAC
2.22.	mITT_LoC		Loss of Control Over Weeks 0-16 vs IgE by Treatment – Fractional Polynomial Model (Secondary Estimand)		ETP, SAC

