## 2.6. Sample Size Calculations

With 70 evaluable participants per arm and assuming the true proportion with loss of control on placebo is 44%, the smallest observed difference that would lead to rejection of the null hypothesis (minimum detectable effect) is 36% corresponding to a proportion with loss of control on GSK3772847 of 28%.

As detailed in Section 2.1, there was a typographical error in the protocol which meant that minimum detectable effect was incorrectly reported as 31%, this has been corrected above.

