## 5.4. Examination of Covariates, Other Strata and Subgroups

### 5.4.1. Covariates and Other Strata

The list of covariates and other strata may be used in descriptive summaries and statistical analyses, some of which may also be used for subgroup analyses. Additional covariates and other strata of clinical interest may also be considered.

Category	Covariates
Screening eosinophils	
At randomisation participants are stratified according to their screening peripheral blood eosinophil count. Screening eosinophils will be included in both primary and secondary analysis as a categorical variable (<150 cells/<math>\mu</math>L, <math>\geq</math>150 cells/<math>\mu</math>L).
 
If the analysis models are unable to converge due to low number of participants with screening blood eosinophils <150 cells/<math>\mu</math>L, then screening eosinophil will be re-categorised according to a cut point of 300 cells/<math>\mu</math>L instead i.e. <300 cells/<math>\mu</math>L and <math>\geq</math>300 cells/<math>\mu</math>L

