- The posterior probabilities that the ratio of the proportion of subjects with loss of asthma control on GSK3772847 compared with placebo is less than 1.0, 0.75, 0.7, 0.5 and 0.2 (i.e. more than a 0%, 25%, 30%, 50% and 80% reduction), and greater than 0.6 (i.e. less than a 40% reduction) will be calculated, along with the estimated median ratio and associated 95% credible interval. The 95% credible interval will use the highest posterior density where possible, and if this isn't possible then the 2.5% and 97.5% credible intervals will be reported.
- In addition to summary tables a plot of the cumulative probabilities from the posterior distribution for the ratio of the proportion of subjects with loss of asthma control on GSK3772847 compared with placebo will be generated.
- This analysis will be repeated for loss of asthma control between Weeks 0 and 6.

Frequentist Method (Supportive):

- The proportion of participants with loss of asthma control will be analysed using logistic regression allowing for screening eosinophils strata. It will include fixed effects terms for treatment and screening eosinophil strata.

Fractional Polynomials (Exploratory Analysis for Loss of Control Over Weeks 0-16):

- Screening blood eosinophil count will be transformed using a first order fractional polynomial term, and then a second order fractional polynomial term which will be included in the model as a continuous covariate. A treatment group by transformed eosinophil covariate interaction will also be included in the model to allow the magnitude of the treatment difference to differ by screening eosinophil count.
- The impact of extreme observations are a well-known problem with fraction polynomial modelling. To address this a two-step transformation to “pull-in” extremes and shift the origin away from zero will be used (Royston and Sauerbrei, 2007). The formula to achieve this is given below:

$$g\delta(x) = \delta + (1 - \delta) \frac{g(x) - g(x_{(1)})}{g(x_{(1)}) - g(x_{(2)})}$$

$$\text{where } g(x) = \left[ \ln \left( \frac{\Phi\left(\frac{(x-\mu)}{\delta}\right) + \varepsilon}{1 - \Phi\left(\frac{(x-\mu)}{\delta}\right) + \varepsilon} \right) + \varepsilon^* \right] / (2\varepsilon^*)$$

with:  $0 < \delta < 1$

$$\varepsilon = 0.01$$

$$\varepsilon^* = -\ln [\varepsilon / (1 + \varepsilon)]$$

$$\bar{x} = n^{-1} \sum x_i$$

$$s = (n - 1)^{-1} \sum (x_{(i)} - \bar{x})^2$$

As recommended we shall use  $\varepsilon = 0.01$  and  $\delta = 0.2$ .

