- All models (first and second order) will be evaluated and the best fitting model will be selected based on the Akaike information criterion (AIC).
- The selected best fitting model will be used to predict the probability of loss of control by treatment arm along with the corresponding predicted odds ratio by screening eosinophil count. This model will include the observed margins (OM) option which will use the analysis dataset.
- The fit of the model to the raw data will be assessed visually by overlaying a plot of the treatment estimates and differences estimated in groups defined by quartiles of screening eosinophil counts. Estimates will be plotted against the mean eosinophil count within each subgroup.
- The role of baseline immunoglobulin E (IgE) and baseline FeNO (separately) on the effectiveness of GSK3772847 with respect to loss of asthma control will be investigated in a similar way.

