## 12.10.9. Pharmacodynamic and Biomarker Tables

Pharmacodynamic and Biomarker: Tables					
No.	Population	IDSL / Example Shell	Title	Programming Notes	Deliverable [Priority]
Secondary: Pharmacodynamic					
6.1.	mITT		Summary of Raw and Percentage Change from Baseline in Free Soluble ST2 concentration (ug/L) (On-treatment)	Pre and Post dose.	ETP, SAC
6.2.	mITT		Analysis of Percentage Change from Baseline in Free Soluble ST2 concentration (ug/mL) (On-treatment)	Pre dose only.	ETP, SAC
6.3.	mITT		Summary of Raw and Percentage Change from Baseline in Free soluble ST2 concentration (ug/L) (Post-treatment)		ETP, SAC
6.4.	mITT		Analysis of Percentage Change from Baseline in Free soluble ST2 concentration (ug/mL) (Post-treatment)		ETP, SAC
6.5.	mITT		Summary of Raw and Percentage Change from Baseline in Total Soluble ST2 concentration (ug/L) (On-treatment)	Pre and Post dose.	ETP, SAC
6.6.	mITT		Analysis of Percentage Change from Baseline in Total Soluble ST2 concentration (ug/L) (On-treatment)	Pre dose only.	ETP, SAC
6.7.	mITT		Summary of Raw and Percentage Change from Baseline in Total Soluble ST2 concentration (ug/L) (Post-treatment)		ETP, SAC
6.8.	mITT		Analysis of Percentage Change from Baseline in Total Soluble ST2 concentration (ug/L) (Post-treatment)		ETP, SAC
Exploratory: Biomarkers					
6.9.	mITT		Summary and Change from Baseline in Induced Sputum Biomarkers (subset) at Weeks 8 and 16	Include geometric mean and %CV	ETP, SAC
6.10.	mITT		Summary and Change from Baseline in Exploratory Serum Markers at Weeks 8 and 16	Include geometric mean and %CV	ETP, SAC

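### The fractional-polynomial pre-transformation divides by the sample variance instead of the standard deviation, so in cells/µL it does not pull in extreme eosinophil values

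*SAP*

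**What the plan says.** Section and figure numbers here are those of the amended plan; the original plan reproduced after it does not contain this formula.

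Sections 7.1.5.1 (loss of control over Weeks 0-16), 7.2.4.1 (FEV1 at Week 4) and 10.1.5 (baseline free sST2) describe the same preliminary step before the fractional polynomials are fitted. Its purpose is explicit: "To address this a two-step transformation to “pull-in” extremes and shift the origin away from zero will be used". The constants are fixed: "As recommended we shall use $\varepsilon = 0.01$ and $\delta = 0.2".

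All three sections define s as (n − 1)^-1 Σ(x_i − x̄)². The copy in 7.2.4.1 is the most legible and shows s as the divisor inside the normal distribution function, Φ((x − x̄)/s).

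For IgE and FeNO, 7.1.5.1 says that their role "with respect to loss of asthma control will be investigated in a similar way". Section 12.10.6 lists the resulting figures, beginning with "Loss of Control Over Weeks 0-16 vs Eosinophils by Treatment – Fractional Polynomial Model (Primary Estimand" (Figure 2.12). Figures 6.9-6.12 in 12.10.11 do the same for free sST2.

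**The concern.** The printed s is the sample variance; its square root is the standard deviation. Dividing a deviation by a variance leaves a quantity in units of 1/x, so the same data give a different transformation when reported in a different unit. Where the numerical spread is large, as with eosinophils in cells/µL, the argument of Φ stays close to 0 for everybody. Φ is nearly linear there, so no pull-in takes place.

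At stake is a safeguard that the plan itself regards as necessary, since it describes extreme observations as a known problem for this type of model. A programmer who follows the text would produce exploratory curves without that protection. For a biomarker whose unit is not settled, the curve would also depend on the unit chosen.

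**Working it through.** **Inputs from the SAP.** ε = 0.01 and δ = 0.2 (7.1.5.1). ε* = −ln(0.01/1.01) = 4.615. Eosinophils are in cells/µL, with cut points 150 and 300 (5.4.1: "Screening eosinophils will be included in both primary and secondary analysis as a categorical variable"). n = 2 × 70 = 140 (2.6: "With 70 evaluable participants per arm").

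**Assumptions, not in the SAP.** Biomarkers are log-normal. Eosinophil median/log-SD is 200/0.6, 250/0.8 or 300/1.0; FeNO 25 ppb/0.7; IgE 150 with log-SD 1.3 or 1.4; free sST2 10 ug/L/0.5.

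**Formula used.** g(x) = [ln{(Φ + ε)/(1 − Φ + ε)} + ε*]/(2ε*), with Φ evaluated at (x − x̄)/s, then rescaled linearly so that the minimum maps to 0.2 and the maximum to 1.

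**Step 1: is the rest of the formula coherent?** At Φ = 0, g = (−4.615 + 4.615)/9.230 = 0. At Φ = 1, g = (4.615 + 4.615)/9.230 = 1. It is; only s is at issue.

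**Step 2: algebra.** For x = x̄ + k·SD the printed definition gives an argument of k·SD/SD² = k/SD. For k = 6:
- SD 100: 0.06, Φ = 0.524
- SD 250: 0.024, Φ = 0.510
- SD 500: 0.012, Φ = 0.505

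With s as the SD the argument is 6 in every case. If the unit changes so that x becomes cx, the printed argument is multiplied by 1/c; with the SD it does not change.

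**Step 3: one simulated eosinophil sample of 140 per scenario, cells/µL.**

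| Median/log-SD | Sample SD | Printed s | Largest argument, printed / SD | Max departure from straight line, printed / SD | Skewness, raw / printed / SD |
|---|---|---|---|---|---|
| 200/0.6 | 126 | 15,943 | 0.044 / 5.6 | 0.00002 / 0.29 | 2.22 / 2.22 / 1.17 |
| 250/0.8 | 372 | 138,530 | 0.019 / 7.2 | 0.00000 / 0.41 | 4.52 / 4.52 / 2.40 |
| 300/1.0 | 404 | 163,000 | 0.013 / 5.2 | 0.00000 / 0.28 | 2.26 / 2.26 / 1.48 |

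The gap between the two largest transformed values is 0.10 to 0.19 as printed and at most 0.0005 with the SD.

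**Step 4: share of the transformed range above the 95th percentile, 500 samples of 140.**

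| Biomarker | As printed | Untransformed | With SD |
|---|---|---|---|
| Eosinophils 200/0.6 | 46% | 46% | 22% |
| Eosinophils 250/0.8 | 55% | 55% | 26% |
| Eosinophils 300/1.0 | 61% | 61% | 29% |
| FeNO 25/0.7 | 50% | – | 24% |
| IgE 150/1.4 | 72% | – | 41% |

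In single samples the printed transformation departs from a straight line by at most 0.0004 for FeNO and by 0.00000 for IgE (log-SD 1.3).

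**Step 5: unit dependence for free sST2.** Section 12.10.9 gives two units that differ by a factor of 1,000: "Summary of Raw and Percentage Change from Baseline in Free Soluble ST2 concentration (ug/L) (On-treatment" (Table 6.1) and "Analysis of Percentage Change from Baseline in Free Soluble ST2 concentration (ug/mL) (On-treatment" (Table 6.2). In one sample in ug/L the printed transformation is nearly linear (largest argument 0.63, departure 0.004). With the same data in ug/mL the largest argument is 634, and every participant falls at one end of the scale (below 0.21 or above 0.99). With the SD the two units give identical results.

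**The case against.** **Extraction.** Other symbols in these formulas are damaged in the text: inside Φ, 7.1.5.1 shows μ and δ where 7.2.4.1 shows x̄ and s. A lost root sign cannot be fully excluded. However, s reads the same in all three sections with both exponents intact, which makes that unlikely. The program may already use the SD; the text would then still need correcting.

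**The figures are the plan's only look at effect modification.** A reader might infer this, but it goes too far. Sections 7.1.5.1, 7.2.4.1 and 10.1.5 overlay treatment estimates and differences by biomarker quartile. Those do not depend on s and give a partial visual check. Section 5.4.1 also leaves room for subgroup analyses.

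**They replaced the protocol's analysis by stratum.** Table 1 does not say so. The split models gave way to the stratum as a covariate, and the polynomials were an addition.

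**Every fractional-polynomial figure is affected.** The method text covers loss of control over Weeks 0-16 against eosinophils, IgE and FeNO, FEV1 at Week 4 against eosinophils, and loss of control against free sST2. For Figures 2.16-2.19 (Weeks 0-6) and 2.30-2.33 (FEV1 against IgE and FeNO), use of the formula is inferred.

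**The curves will be driven by a few high values.** This was not shown. A power is applied after the transformation, and leverage depends on it. For eosinophils 250/0.8 as printed, the top-5% share is 55% at power 1 but 37% on the log scale. Neither AIC selection nor the odds-ratio curves were simulated.

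**Conclusion.** Wrong as written; minor to moderate. The unit dependence follows from the algebra and needs no distributional assumption. That nothing is pulled in with eosinophils in cells/µL holds for any plausible SD; the percentages rest on the assumed log-normal distributions and n = 140. Of the two stated aims, limiting extremes is not met in the SAP's own eosinophil unit, while shifting the origin away from zero is.

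A reader might infer that efficacy conclusions are at risk. They are not: the primary Bayesian, supportive logistic, Kaplan-Meier and repeated-measures analyses do not use s. Nor should the behaviour in 10^9/L be read as a defect of the planned eosinophil figures, because the SAP uses only cells/µL. The unit matters in practice for free sST2, where the plan's own table titles disagree.

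**What to change.** In 7.1.5.1, 7.2.4.1 and 10.1.5, define s = √[(n − 1)^-1 Σ(x_i − x̄)²]. Keep ε = 0.01 and δ = 0.2. Confirm that the program uses this definition, and regenerate any fractional-polynomial figure that was produced with the variance. Separately, reconcile the ug/L and ug/mL labels for free sST2 in 12.10.9.

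The cost is one corrected line in three places and a code check. It needs no new data and involves no trade-off.

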**CONFIDENTIAL**

207597

Efficacy: Figures					
No.	Population	IDSL / Example Shell	Title	Programming Notes	Deliverable [Priority]
2.23.	mITT_LoC		Loss of Control Over Weeks 0-16 vs IgE – Fractional Polynomial Treatment Difference (Secondary Estimand)		ETP, SAC
2.24.	mITT_LoC		Loss of Control Over Weeks 0-16 vs FeNO by Treatment – Fractional Polynomial Model (Primary Estimand)		ETP, SAC
2.25.	mITT_LoC		Loss of Control Over Weeks 0-16 vs FeNO – Fractional Polynomial Treatment Difference (Primary Estimand)		ETP, SAC
2.26.	mITT_LoC		Loss of Control Over Weeks 0-16 vs FeNO by Treatment – Fractional Polynomial Model (Secondary Estimand)		ETP, SAC
2.27.	mITT_LoC		Loss of Control Over Weeks 0-16 vs FeNO – Fractional Polynomial Treatment Difference (Secondary Estimand)		ETP, SAC
Secondary Endpoint: Exploratory Analysis of FEV1					
2.28.	mITT		FEV1 at Week 4 vs Eosinophils by Treatment – Fractional Polynomial Model		ETP, SAC
2.29.	mITT		FEV1 at Week 4 vs Eosinophils – Fractional Polynomial Treatment Difference		ETP, SAC
2.30.	mITT		FEV1 at Week 4 vs IgE by Treatment – Fractional Polynomial Model		ETP, SAC
2.31.	mITT		FEV1 at Week 4 vs IgE – Fractional Polynomial Treatment Difference		ETP, SAC
2.32.	mITT		FEV1 at Week 4 vs FeNO by Treatment – Fractional Polynomial Model		ETP, SAC
2.33.	mITT		FEV1 at Week 4 vs FeNO – Fractional Polynomial Treatment Difference		ETP, SAC

## 12.10.7. Safety Tables

Safety: Tables					
No.	Population	IDSL / Example Shell	Title	Programming Notes	Deliverable [Priority]
Adverse Events (AEs)					
3.1.	SAFF_ALL	SAFE_T01	Overview of On-treatment Adverse Events During the Study		ETP, SAC
3.2.	SAFF_ALL	AE1	Summary of All On-treatment Adverse Events by System Organ Class and Preferred Term	ICH E3	ETP, SAC
3.3.	SAFF_ALL	AE1	Summary of All Post-treatment Adverse Events by System Organ Class and Preferred Term	ICH E3	ETP, SAC
3.4.	SAFF_ALL	AE1	Summary of All On-treatment Adverse Events Leading to Permanent Discontinuation of Study Treatment by System Organ Class and Preferred Term	ICH E3	ETP, SAC
3.5.	SAFF_ALL	AE1	Summary of All On-treatment Adverse Events Leading to Withdrawal from Study by System Organ Class and Preferred Term	ICH E3	ETP, SAC
3.6.	SAFF_ALL	AE1	Summary of All On-treatment Fatal Adverse Events by System Organ Class and Preferred Term	ICH E3	ETP, SAC
3.7.	SAFF_ALL	AE3	Summary of All On-treatment Common ( $\geq 3\%$ ) Adverse Events by Overall Frequency	ICH E3	ETP, SAC
3.8.	SAFF_ALL	AE1	Summary of All On-treatment Drug-Related Adverse Events by System Organ Class and Preferred Term	ICH E3	ETP, SAC
3.9.	SAFF_ALL	AE15	Summary of All On-treatment Common ( $\geq 3\%$ ) Non-serious Adverse Events by System Organ Class and Preferred Term (Number of Participant and Occurrences)	FDAAA, EudraCT	ETP, SAC
3.10.	SAFF_ALL	AE1	Summary of All Pre-treatment Serious Adverse Events by System Organ Class and Preferred Term		ETP, SAC

Safety: Tables					
No.	Population	IDSL / Example Shell	Title	Programming Notes	Deliverable [Priority]
3.11.	SAFF_ALL	AE1	Summary of All On-treatment Serious Adverse Events by System Organ Class and Preferred Term	ICH E3	ETP, SAC
3.12.	SAFF_ALL	AE1	Summary of All Post-treatment Serious Adverse Events by System Organ Class and Preferred Term	ICH E3	ETP, SAC
3.13.	SAFF_ALL	AE16	Summary of All On-treatment Serious Adverse Events by System Organ Class and Preferred Term (Number of Participants and Occurrences)	FDAAA, EudraCT	ETP, SAC
3.14.	SAFF_ALL	AE1	Summary of All On-treatment Serious Adverse Events Leading to Permanent Discontinuation of Study Treatment by System Organ Class and Preferred Term	IDSL	ETP, SAC
3.15.	SAFF_ALL	AE1	Summary of All On-treatment Serious Adverse Events Leading to Withdrawal from Study by System Organ Class and Preferred Term	IDSL	ETP, SAC
Adverse Events of Special Interest (AESIs)					
3.16.	SAFF_ALL	AE1	Summary of On-treatment Adverse Events of Special Interest	IDSL	ETP, SAC
3.17.	SAFF_ALL	AE1	Summary of On-treatment Serious Adverse Events of Special Interest	IDSL	ETP, SAC
3.18.	SAFF_ALL	AE1	Summary of Post-treatment Adverse Events of Special Interest	IDSL	ETP, SAC
3.19.	SAFF_ALL	AE1	Summary of Post-treatment Serious Adverse Events of Special Interest	IDSL	ETP, SAC
Mexico Specific Tables					
3.20.	SAFF_ALL		Summary of Suspected Investigational Product Adverse Reaction (Mexican Participants Only)		ETP, SAC
3.21.	SAFF_ALL		Summary of Suspected Investigational Product Adverse Reaction (Non-Mexican Participants)		ETP, SAC

Safety: Tables					
No.	Population	IDSL / Example Shell	Title	Programming Notes	Deliverable [Priority]
Laboratory: Chemistry					
3.22.	SAFF_ALL	LB1	Summary of Clinical Chemistry	ICH E3	ETP, SAC
3.23.	SAFF_ALL	LB1	Summary of Change from Baseline in Clinical Chemistry	ICH E3	ETP, SAC
3.24.	SAFF_ALL	LB16	Summary of Worst Case Chemistry Results Relative to Normal Range Post-Baseline Relative to Baseline	ICH E3	ETP, SAC
Laboratory: Hematology and Cardiac Markers					
3.25.	SAFF_ALL	LB1	Summary of Hematology and Cardiac Markers	ICH E3	ETP, SAC
3.26.	SAFF_ALL	LB1	Summary of Changes from Baseline in Hematology and Cardiac Markers	ICH E3	ETP, SAC
3.27.	SAFF_ALL	LB16	Summary of Worst Case Hematology and Cardiac Markers Results Relative to Normal Range Post-Baseline Relative to Baseline	ICH E3	ETP, SAC
Laboratory: Hepatobiliary (Liver)					
3.28.	SAFF_ALL	LIVER1	Summary of Liver Monitoring/Stopping Event Reporting	IDSL	ETP, SAC
3.29.	SAFF_ALL	LIVER10	Summary of Hepatobiliary Laboratory Abnormalities	IDSL	ETP, SAC
ECG					
3.30.	SAFF_ALL		Summary of Antihistamine, Decongestant and Caffeine Use Prior to ECG assessments		ETP, SAC
3.31.	SAFF_ALL	EG1	Summary of ECG Findings	IDSL	ETP, SAC
3.32.	SAFF_ALL	EG2	Summary of ECG Values by Visit	IDSL	ETP, SAC

Safety: Tables					
No.	Population	IDSL / Example Shell	Title	Programming Notes	Deliverable [Priority]
3.33.	SAFF_ALL	EG2	Summary of Change from Baseline in ECG Values by Visit	IDSL	ETP, SAC
3.34.	SAFF_ALL	EG10	Summary of Maximum QTcF Values Post-Baseline Relative to Baseline by Category	IDSL	ETP, SAC
3.35.	SAFF_ALL	EG11	Summary of Maximum Increase in QTcF Values Post-Baseline Relative to Baseline by Category	IDSL	ETP, SAC
Holter					
3.36.	SAFF_ALL	HM1	Summary of Holter Interpretations	IDSL	ETP, SAC
3.37.	SAFF_ALL	HM2	Summary of Holter Abnormalities	IDSL	ETP, SAC
3.38.	SAFF_ALL	HM3	Summary of Holter Values	IDSL	ETP, SAC
3.39.	SAFF_ALL	HM3	Summary of Change from Baseline in Holter Values	IDSL	ETP, SAC
3.40.	SAFF_ALL	HM4	Summary of Subjects with R-on-T Beats	IDSL	ETP, SAC
Vital Signs					
3.41.	SAFF_ALL	VS1	Summary of Vital Signs	ICH E3	ETP, SAC
3.42.	SAFF_ALL	VS1	Summary of Change from Baseline in Vital Signs	ICH E3	ETP, SAC
3.43.	SAFF_ALL	VS1	Summary of Change from Pre-dose to Post-dose in Vital Signs	ICH E3	ETP, SAC

